3.3 SELECTION OF TRIAL POPULATION

In order to test the two combined efficacy-safety hypotheses in NVAF patients that have undergone a successful PCI, at least 834 patients per treatment group are estimated to be required (see [Section 7.6](#)).

Approximately 550 trial centres worldwide will participate in the trial. The enrolment target for each site is a minimum of one patient every two months. Enrolment will be competitive and the trial will be terminated when the total number of events has been observed, regardless of enrolment at individual centres. If enrolment is delayed, additional study centres may be recruited.

A log of all patients included into the study (i.e. having given informed consent) will be maintained in the Investigator Site File (ISF) at the investigational site irrespective of whether they have been treated with investigational drug or not.

3.3.1 Main diagnosis for study entry

3.3.2 Inclusion criteria

The patient must meet all the inclusion criteria:

1. Male or female patients aged ≥ 18 years
2. Patients with NVAF that have been receiving oral anticoagulant treatment (either with warfarin, another VKA or other novel oral anticoagulant), or were treatment naïve prior to PCI. AF may be paroxysmal, persistent or permanent, and not secondary to a

Proprietary confidential information.

© 2016 Boehringer Ingelheim International GmbH or one or more of its affiliated companies. All rights reserved.

This document may not - in full or in part - be passed on, reproduced, published or otherwise used without prior written permission.

reversible disorder such as MI, pulmonary embolism, recent surgery, pericarditis or thyrotoxicosis, unless long term oral anticoagulation is planned

3. Patient presenting with:

- An ACS (STEMI, NonSTEMI [NSTEMI] or unstable angina [UA]) that was successfully¹ treated by PCI and stenting (either BMS or DES)

Or

- Stable Coronary Artery Disease with at least one lesion eligible for PCI that was successfully¹ treated by elective² PCI and stenting (either BMS or DES)

4. The patient must be able to give informed consent in accordance with International Conference on Harmonisation (ICH) Good Clinical Practice (GCP) guidelines and local legislation and/or regulations.

3.3.3 Exclusion criteria

The patient must not meet any of the exclusion criteria:

1. Patients with a mechanical or biological heart valve prosthesis
2. Cardiogenic shock during current hospitalisation
3. Patients who have used fibrinolytic agents within 24 hours of randomisation that, in the opinion of the Investigator, will put the patient at high risk of bleeding
4. Stroke within 1 month prior to screening visit
5. Patients, who in the opinion of the Investigator, have had major surgery within the month prior to screening
6. Patient has received an organ transplant or is on a waiting list for an organ transplant
7. History of intraocular, spinal, retroperitoneal or a traumatic intra-articular bleeding unless the causative factor has been permanently eliminated or repaired (e.g. by surgery)
8. Gastrointestinal (GI) haemorrhage within one month prior to screening, unless, in the opinion of the Investigator, the cause has been permanently eliminated (e.g. by surgery)

¹ Successful treatment with PCI is defined as achievement of < 30 % residual diameter stenosis of the target lesion assessed by visual inspection or quantitative coronary angiography and no in-hospital major adverse cardiac events (MI or repeat coronary revascularisation of the target lesion).

² Indication for elective PCI should be based upon the ACCF/SCAI/STS/AATS/AHA/ASNC [\[R14-1287\]](#) and ESC guidelines [\[P10-12773\]](#).

Proprietary confidential information.

© 2016 Boehringer Ingelheim International GmbH or one or more of its affiliated companies. All rights reserved.

This document may not - in full or in part - be passed on, reproduced, published or otherwise used without prior written permission.

9. Major bleeding episode (reduction in the haemoglobin level of at least 2g/dL, transfusion of at least two units of blood, or symptomatic bleeding in a critical area or organ) including life-threatening bleeding episode (symptomatic intracranial bleeding, bleeding with a decrease in the haemoglobin level of at least 5g/dL or bleeding requiring transfusion of at least 4 units of blood or inotropic agents or necessitating surgery) in one month prior to screening visit
10. Haemorrhagic disorder or bleeding diathesis (e.g. von Willebrand disease, haemophilia A or B or other hereditary bleeding disorder, history of spontaneous intra-articular bleeding, history of prolonged bleeding after surgery/intervention)
11. Anaemia (haemoglobin <10g/dL) or thrombocytopenia including heparin-induced thrombocytopenia (platelet count <100 × 10⁹/L) at screening (Visit 1)
12. Severe renal impairment (estimated CrCl calculated by Cockcroft-Gault equation) <30mL/min at screening (Visit 1)
13. Active liver disease as indicated by at least one of the following:
 - Prior and persistent alanine aminotransferase (ALT) **or** Aspartate transaminase (AST) **or** alkaline phosphatase (AP) >3 × upper limit of normal (ULN)¹
 - Known active hepatitis C
 - Known active hepatitis B
 - Known active hepatitis A
14. Recent malignancy or radiation therapy (≤6 months) unless, in the opinion of the Investigator, the estimated life expectancy is greater than 36 months
15. Need for continued treatment with systemic ketoconazole, itraconazole, posaconazole, cyclosporine, tacrolimus, dronedarone, rifampicin, phenytoin, carbamazepine, St. John's Wort. See [Section 4.2.2](#)
16. Patients who, in the Investigator's opinion, need continuous treatment with Non-Steroidal Anti-Inflammatory Drugs (NSAIDs)
17. Patients with a known allergy to dabigatran etexilate or to the excipients used for the capsule of the drug
18. Patients with a known allergy to warfarin tablets or to the excipients
19. Patients who, in the Investigator's opinion, should not be treated with OAC
20. Patients with a contraindication to clopidogrel, ticagrelor or ASA

¹ Clinical judgement of whether ALT/AST enzyme elevation is due to active liver disease or due to ACS, should be made by the Investigator following evaluation the of the clinical characteristics of the patient and the laboratory findings.

21. Pre-menopausal women (last menstruation \leq 1 year prior to screening) who:

- Are pregnant or breast feeding or
- Are not surgically sterile or
- Are of child bearing potential and not practising two acceptable methods of birth control, or do not plan to continue practising an acceptable method of birth control throughout the trial. Acceptable methods of birth control are oral or parenteral (patch, injection, implant) hormonal contraception which has been used continuously for at least one month prior to the first dose of study medication, intrauterine device or intrauterine system, double-barrier method of contraception (condom and occlusive cap or condom and spermicidal agent), male sterilisation and complete sexual abstinence (if acceptable by local authorities). Periodic abstinence is not an acceptable method of contraception.

22. Patients who have participated in another trial with an investigational drug or device within the past 30 days preceding the screening visit or are participating in another trial (patients participating in an observational study only will not be excluded)

23. Patients not willing or able to comply with the protocol requirements or considered unreliable by the Investigator concerning the requirements for follow-up during the study and/or compliance with study drug administration, who have a life expectancy less than the expected duration of the trial due to concomitant disease, or who have any condition which in the opinion of the Investigator, would not allow safe participation in the study (e.g. drug addiction, alcohol abuse).

3.3.4 Removal of patients from therapy or assessments

3.3.4.1 Removal of individual patients

An individual patient is to be withdrawn from the trial if:

- The patient withdraws consent, without the need to justify the decision

Treatment with study drugs should be discontinued if:

- The patient needs to take concomitant drugs that interfere with the investigational product or other study medication(s)
- The patient is no longer able to take trial medication for other medical reasons (e.g. surgery, AEs, or other diseases)
- The patient is persistently noncompliant with study drug administration
- If a patient becomes pregnant during the trial the investigational drug will be stopped, the patient will be discontinued from the trial medication and the patient will be followed up until birth or otherwise termination of the pregnancy. For further

Proprietary confidential information.

© 2016 Boehringer Ingelheim International GmbH or one or more of its affiliated companies. All rights reserved.

This document may not - in full or in part - be passed on, reproduced, published or otherwise used without prior written permission.

information, including the process for follow-up on the outcome of the pregnancy please see [Section 5.2.2.3](#).

- Patients on dabigatran etexilate who are found to have a CrCl <30mL/min during the course of the trial, should have study medication stopped and a parenteral anticoagulant can be started according to local practice (see [Appendix 10.1](#) for switching to a parenteral anticoagulant). CrCl laboratory testing should be repeated as soon as feasible, ideally within 48 hours. If this second measurement confirms a CrCl <30mL the patient should be permanently discontinued from dabigatran etexilate, unless the concomitant clinical condition is expected to allow recovery of the renal function within 7 days from the initial CrCl reduction. A patient should also be permanently discontinued from study drug, if CrCl drops to <30mL/min at two different occasions during the trial
- In the opinion of the Investigator, continuation on the study drug is not in the patient's best interest, if eligibility criteria are being violated, or if the patient fails to comply with the protocol (e.g. non-attendance at trial assessments)
- The patient elects to stop taking study drug (the patient should be encouraged to resume study drug per the protocol).

Patients who discontinue treatment prematurely will be followed up until the end of the study (for further details please see [Sections 6.2.2 and 6.2.3](#)).

Patients who drop out during the screening phase prior to randomisation (Visit 2) will be considered a screen failure. They have to be recorded as screen failures in the electronic Case Report Forms (eCRFs), along with the reason for failing screening, and no further follow-up is required.

Patients who discontinue or withdraw from the study after randomisation (Visit 2) will be considered as "early discontinuations" and the reason for premature discontinuation must be recorded in the eCRFs. The data will be included in the trial database and will be reported.

Patients who withdraw or discontinue from the trial after randomisation will not be replaced.

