Note: In patients where renal function is impaired or procedures undertaken which may temporarily compromise renal function, a serum creatinine should be performed and CrCl calculated based on the Cockcroft-Gault formula. In patients receiving dabigatran etexilate, if CrCl drops to <30mL/min during the course of the study, study medication should be stopped and bridging therapy may be considered. Study drug dabigatran etexilate can be re-started if CrCl recovers to ≥ 30 mL/min within seven days; otherwise it should be permanently discontinued for the duration of the trial and the patient followed until the trial completes. A patient should also be permanently discontinued from study drug, if CrCl drops to <30mL/min at two different occasions during the trial. See [Section 3.3.4.1](#).

Warfarin Treated Group:

Preoperative Phase:

Bridging therapy with a parenteral anticoagulant should be considered depending on the length of study drug interruption. Bridging therapy is at the discretion of the Investigator and can be performed according to local practice (see [Appendix 10.1](#) for guidance).

Post Procedural Period:

Anticoagulation can be started as soon as clinically feasible with i.v. (unfractionated) or s.c. LMWH and simultaneously with study warfarin until the INR is ≥ 2.0 . Parenteral bridging therapy should be stopped when target INR is achieved (see Appendix 10.1 for guidance).

Spinal Anaesthesia/Epidural Anaesthesia/Lumbar Puncture

Dabigatran and Warfarin Treated Group:

Procedures such as spinal anaesthesia may require complete haemostatic function. See [Table 4.2.1.3: 1](#) for recommendations on when to stop dabigatran before spinal/epidural anaesthesia. For patients randomised to Warfarin, INR measurements should be performed to ensure that coagulation is under control.

The risk of spinal or epidural haematoma may be increased in cases of traumatic or repeated puncture and by the prolonged use of epidural catheters. After removal of a catheter, resume treatment with study medication after complete haemostasis is achieved, but at minimum an interval of at least one hour should elapse for all patients. These patients require frequent observation for neurological signs and symptoms of spinal or epidural haematoma.

Proprietary confidential information.

© 2016 Boehringer Ingelheim International GmbH or one or more of its affiliated companies. All rights reserved.

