D3.1	Mandatory medication not taken per protocol (ASA)	ASA not taken for the first month for warfarin patients with a BMS or for the first three months for patients with a DES as indicated on the Trial Medication Compliance eCRF page (exclude if at least one visit is ticked "No").	PPS, but only from start of non-compliance onwards
D3.2	Mandatory medication not taken per protocol (clopidogrel/ticagrelor)	Clopidogrel/ticagrelor non-compliance during the first 12 months of treatment as indicated on the Trial Medication Compliance eCRF page (exclude if at least one visit is ticked "No").	PPS, but only from start of non-compliance onwards
G	Trial Specific Protocol Violations		
G1	Patient not withdrawn from treatment if CrCl drops to <30mL/min at two different occasions during the trial	As per study protocol, this only applies to patients randomised to dabigatran etexilate.	PPS

KEY: PPS – Per Protocol Set

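### Protocol 3.3.4.1 and 4.2.1.3 give conflicting seven-day rules for permanently stopping dabigatran after CrCl <30 mL/min, and SAP violation G1 tests neither

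*Protocol*

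**What the plan says.** **Protocol 3.3.4.1** (removal of individual patients). A dabigatran patient with CrCl <30 mL/min stops study drug, and the test is repeated, ideally within 48 hours. Then: "If this second measurement confirms a CrCl <30mL the patient should be permanently discontinued from dabigatran etexilate", with the exception "unless the concomitant clinical condition is expected to allow recovery of the renal function within 7 days from the initial CrCl reduction". A further sentence adds: "A patient should also be permanently discontinued from study drug, if CrCl drops to <30mL/min at two different occasions during the trial".

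**Protocol 4.2.1.3** (emergency and elective surgery, Note under the post-procedural period). The Note opens with a limited setting, "In patients where renal function is impaired or procedures undertaken which may temporarily compromise renal function", but its trigger for dabigatran patients is general: "if CrCl drops to <30mL/min during the course of the study, study medication should be stopped and bridging therapy may be considered". On restarting, it says "Study drug dabigatran etexilate can be re-started if CrCl recovers to ≥ 30 mL/min within seven days", and sets the alternative as "within seven days; otherwise it should be permanently discontinued for the duration of the trial and the patient followed until the trial completes". It repeats the two-occasions sentence of 3.3.4.1 word for word and closes by referring the reader to 3.3.4.1.

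**SAP 6.2, Table 6.2:1.** Violation G1 reads "Patient not withdrawn from treatment if CrCl drops to <30mL/min at two different occasions during the trial". It applies only to patients randomised to dabigatran and excludes them from the per-protocol set. Violation C3 separately says that non-compliance arising from a temporary interruption for a CrCl fall below 30 mL/min is not to be counted as a violation.

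**The concern.** One section makes permanence depend on a forecast, the other on an observed value. A site that follows the cross-references reads both, and nothing says which governs. Two patients with the same renal course could therefore be handled differently, one permanently off dabigatran and the other restarted, according to which page the site used.

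The point matters because this is the protocol's renal stopping rule for the test drug. Section 1.2 reports a 6.8-fold increase in AUC in severe renal impairment, and section 2.3 calls treatment contraindicated there. The decision also fixes a patient's last intake of study drug, which sets the censoring date in the on-treatment analyses. Finally, the SAP's only violation category for this rule cannot show whether the seven-day condition was followed in either form.

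**Working it through.** The plan gives no figure to reproduce on this point, so the check is a comparison of texts. Take a first episode in which the repeat confirms CrCl <30 mL/min, and treat the repeat as part of the same occasion. Cross the two things the sections look at: whether recovery was expected within 7 days, and whether it happened.

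| Recovery expected | Recovery seen by day 7 | 3.3.4.1 | 4.2.1.3 | Same result |
|---|---|---|---|---|
| yes | yes | permanent stop not required | restart allowed | yes |
| yes | no | permanent stop not required | permanent stop | no |
| no | yes | permanent stop | restart allowed | no |
| no | no | permanent stop | permanent stop | yes |

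So 2 × 2 = 4 cases, of which 2 differ.

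- **Not expected but achieved.** This is a direct contradiction: one section ends treatment and the other permits it to resume.
- **Expected but not achieved.** The difference is narrower. The drug is already held under both sections, but only 4.2.1.3 makes the stop permanent on day 7. Under 3.3.4.1 a patient who recovers later has not been permanently discontinued by its wording.

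**Unconfirmed falls.** If the repeat, taken inside the seven days, is 30 mL/min or more, 3.3.4.1 does not require a permanent stop and 4.2.1.3 counts the value as recovery. The sections agree.

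**Second separate occasion.** Both sections require a permanent stop, in identical words.

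**The confirmatory repeat as an occasion.** Neither section says whether it counts. If it did, every confirmed case would meet the two-occasions clause under both sections, and the exception in 3.3.4.1 could never operate. That makes the reading unlikely, but the text does not exclude it.

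**G1.** In a first episode, with the repeat not counted, G1 flags none of the four cases, even if dabigatran was continued or restarted against one of the seven-day rules. After two occasions it flags non-withdrawal whichever section is read. C3 does not fill the gap, since it only excuses temporary interruptions.

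**Analyses reached.** The primary analysis is on the full analysis set as randomised (SAP 7.4), with follow-up to the end of the trial after discontinuation. Neither membership of that set nor its censoring rules depend on the renal rule. The on-treatment analyses censor premature stoppers at last intake plus 6 days and ignore temporary gaps. A patient who restarts therefore stays at risk across the gap, while one who is stopped permanently leaves 6 days after the last dose. The per-protocol set is affected through G1.

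**The case against.** The best defence is that 3.3.4.1 is the lead section. The elective surgery text, the first footnote to Table 4.2.1.3:1, the Note itself and section 5.2.3 all point to it, and the Note sits under a post-procedural heading. The two can also be read in sequence: expectation decides whether to hold or end treatment, and actual recovery then decides restart. This has some force and covers most cases. But no text states the sequence, the Note's trigger is not confined to surgery, and the sequence fails where recovery was not expected but occurs. There 3.3.4.1 has already required a permanent stop.

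Several stronger readings are tempting and are not supported.

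- A reader might infer that who counts as a violator depends on the section consulted. It does not: G1 follows the clause that is worded identically in both.
- A reader might infer that G1 wrongly flags permitted restarts. If the repeat counts as an occasion, both sections forbid the restart and the flag is correct. If it does not, G1 raises no flag.
- A reader might infer that patients could be dosed while CrCl stays below 30 mL/min. Both sections stop the drug at the first low value, and 4.2.1.3 says such patients should not be receiving it. The conflict is about restarting.
- A reader might want a percentage of patients affected. With equal forecasting accuracy assumed for recoverers and non-recoverers, disagreement among confirmed cases is simply one minus that accuracy. The documents supply no value for it.

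It is also fair to say that the per-protocol analysis may be omitted if fewer than 10% of the treated set are excluded (SAP 6.3).

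**Conclusion.** The concern stands as an inconsistency between two stated rules. For a first confirmed fall they give different permanent-stop results in 2 of 4 cases. One is a plain contradiction and the other a difference in whether an existing hold becomes permanent. G1 is consistent with both sections on the clause they share, but is silent on the seven-day condition in either form.

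The size is modest. The count assumes the confirmatory repeat is not a second occasion. How many patients fall in the two discordant cases cannot be derived from the documents. The primary analysis set and its censoring rules are untouched. The direct analytic effect is on the on-treatment and per-protocol sensitivity analyses, for dabigatran patients only. The main reason to act is that sites need one instruction on permanent discontinuation.

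**What to change.** Reconcile 3.3.4.1 and 4.2.1.3 into one rule, stated once and cross-referenced from the other place. The text should settle three things: whether a confirmatory value is needed, whether the seven-day condition is expected or observed recovery, and whether the confirmatory repeat is a separate occasion. Which rule to adopt is for the sponsor's clinical team.

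Then reword G1 so that it tests the reconciled rule, including a patient kept on or restarted on dabigatran against the seven-day condition.

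The cost is a protocol clarification or amendment wording and one row of the SAP table. No new data collection is needed.

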3.3.4.2 Discontinuation of the trial by the sponsor

BI reserves the right to discontinue the trial overall or at a particular trial site at any time for the following reasons:

1. Advice of the independent DMC, decision by an Independent Ethics Committee (IEC) /Institutional Review Board /(IRB) or Competent Authority (CA)
2. Failure to meet expected enrolment goals overall or at a particular trial site
3. Emergence of any efficacy/safety information that could significantly affect continuation of the trial
4. Violation of GCP, the CTP, or the contract by a trial site or Investigator, disturbing the appropriate conduct of the trial.

Proprietary confidential information.

© 2016 Boehringer Ingelheim International GmbH or one or more of its affiliated companies. All rights reserved.

This document may not - in full or in part - be passed on, reproduced, published or otherwise used without prior written permission.

The Investigator / the trial site will be reimbursed for reasonable expenses incurred in case of trial termination (except in case of the fourth reason).

Proprietary confidential information.

© 2016 Boehringer Ingelheim International GmbH or one or more of its affiliated companies. All rights reserved.

This document may not - in full or in part - be passed on, reproduced, published or otherwise used without prior written permission.

